6.1.3.2 Any Post-Operative Day before the Last Post-Operative Day

On any post-operative day before the Last Post-Operative Day (see Section 6.1.3.3), the following assessments will be performed:

Daily post-operative assessments

The following assessments will be on every post-operative day:

- Vital signs.
- Blood draw for:
 - fibringen plasma levels (local lab-activity; central lab-antigen and activity)
 - safety lab (local-haematology and clinical chemistry)
 - retention plasma samples for potential retesting.
- Wound haematomas and oozing (noting whether surgical evacuation is required and severity and volume of oozing).
- AEs and concomitant medications.

Octafibrin infusion, as required

Additional dosing should occur as required depending on the actual and target plasma level and based on the following criteria:

- If the actual fibrinogen plasma level is below the accepted lower limit of the target fibrinogen plasma level (80 mg/dL for minor surgery, 130 mg/dL for major surgery; see Section 5.4), the subject should receive another infusion of *Octafibrin*.
- If the fibrinogen plasma level is greater than or equal to the accepted lower limit of the target fibrinogen plasma level, *Octafibrin* **should not** be administered on that day.

Pre- and post-infusion assessments

If the subject receives an infusion of *Octafibrin*, the following pre- and post-infusion assessments will be performed:

Pre-infusion assessments:

- Blood draw for:
 - fibringen plasma level (local lab-activity; central lab-antigen and activity)
 - retention plasma samples for potential retesting.

1 hour (± 15 minutes) after the end of each infusion:

- Vital signs.
- Blood draw for:
 - fibringen plasma level (local lab-activity; central lab-antigen and activity)
 - safety lab (local-haematology and clinical chemistry)
 - thrombogenicity
 - retention plasma samples for potential retesting.

6.1.3.3 Last Post-Operative Day

The Last Post-Operative Day is either post-operative day 3 for minor and post-operative day 7 for major surgery or the day of the last post-operative infusion, whichever comes last.

The assessments performed on the Last Post-Operative Day are identical to those performed on any other post-operative day (see Section 6.1.3.2).

In addition, the following assessments will be performed on the Last Post-Operative Day:

- post-operative efficacy assessment by the haematologist (see Section 7.2.2.3).
- brief narrative describing the details of hospitalisation (start and end date, details of the procedure), follow-up, outcome, and efficacy of the intervention.

The assessments performed on the Last Post-Operative Day conclude the surgical observation period. No further study-related assessments will be performed, unless safety concerns (e.g., ongoing AEs) require follow-up.

Patients may remain in the study until the 24th patient has at least one documented bleeding episode. When the study is closed, all subjects will be asked to return for a Study Completion Visit as summarised in Section 6.1.4.

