Fibrinogen antigen			x [a,c]		x [a,c]	x [c]	x [c]	x [c]	x [c]	x [c]	x [c]	x [c]	
Thrombogenicity [c]			х			х			х			х	
Safety lab (haematology and clinical chemistry) [b]		х					х		х	х		х	
Retention plasma samples [d]			х		x [a]	Х	Х	Х	Х	Х	Х	х	
Retention serum samples [d]			x										x
Urine or blood pregnancy test		х											
Infusion of Octafibrin			х		X**		x [e]		x [e]				
Haemostatic efficacy assessments (intra- and postoperative)						x [f]						x [g]	
Wound haematomas and oozing							Х			х			
Narrative of outcome												х	
AEs [h]			>	>	>	>	>	>	>	>	>	>	>
Concomitant medications		>	>	>	>	>	>	>	>	>	>	>	>

AE = adverse event; POP = postoperative.

^{* ≤ 30} minutes before each infusion of Octafibrin.

^{**} If considered necessary.

[#] To be re-reviewed if period between screening and treatment is more than 3 months.

[[]a] ≤ 30 minutes before and after each infusion of Octafibrin .

[[]b] Measured in local laboratories.

[[]c] Measured in central laboratory.

[[]d] Plasma retain sample for potential retesting; serum retain sample for potential viral testing.

[[]e] If the actual fibrinogen plasma level is below the accepted lower limit of the target fibrinogen plasma level, the subject **should** receive another infusion of *Octafibrin*. If the fibrinogen level is greater than or equal to the accepted lower limit of the the target fibrinogen level, *Octafibrin* **should not** be administered.

[[]f] Intraoperative efficacy assessment by surgeon.

[[]g] Postoperative efficacy assessment by haematologist.

[[]h] Including thromboembolic events and hypersensitivity reactions.

PROTOCOL SIGNATURES

This study is intended to be conducted in compliance with the protocol, Good Clinical Practice. and the applicable regulatory requirements.

Signature of the Sponsor's Representative

TABLE OF CONTENTS

	NTRODUCTION	 7
1.1	Background	7
1.2	Octafibrin	7
1.3	RATIONALE FOR CONDUCTING THE STUDY	8
1.4	Dose Rationale	8
1.5	BENEFIT-RISK STATEMENT	9
2 S	TUDY OBJECTIVES	10
2.1	Primary Objective	10
2.2	SECONDARY OBJECTIVES	10
3 II	NVESTIGATIONAL PLAN	11
3.1	PRIMARY AND SECONDARY ENDPOINTS	11

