1 INTRODUCTION

1.1 Background

Human fibrinogen is a plasma glycoprotein synthesised in the liver, and it circulates in the plasma at a concentration of 2.9–4.5 g/L. In healthy human adults, about 2–5 g of fibrinogen is synthesised daily, and the same amount is catabolised [1, 2]. Fibrinogen is essential for haemostasis, wound healing, fibrinolysis, inflammation, angiogenesis, cellular and matrix interactions, and neoplasia. These processes involve the conversion of fibrinogen into fibrin, and often the interaction of fibrinogen with various proteins and cells. The plasma half-life of fibrinogen, under normal physiological conditions, has been estimated to be 3–5 days [3, 4].

The plasma level of clottable fibrinogen may be markedly decreased or even undetectable in various congenital or acquired conditions [5, 6]. Conditions of congenital fibrinogen deficiency include:

- Afibrinogenaemia: Complete absence or extremely low levels of plasma fibrinogen.
- Hypofibrinogenaemia: Reduced concentration of plasma fibrinogen.
- Dysfibrinogenaemia: Presence of abnormal or dysfunctional fibrinogen molecules.

Congenital afibrinogenaemia is a rare inherited autosomal recessive disorder occurring in homozygotic patients with an estimated incidence of 1 in 10⁶ in the European population [7]. The disease is characterised by a complete lack of coagulable and/or immunologically determinable fibrinogen in the plasma. Patients present with frequent severe bleeding episodes since birth or early childhood [8, 9]. Bleeding may occur after a minor trauma or a small surgical intervention, into the skin, mucosa, muscles, gastrointestinal tract, or the brain.

Congenital hypofibrinogenaemia is more common than afibrinogenaemia and is characterised by low but measurable fibrinogen plasma levels. Clinical symptoms of hypofibrinogenaemia are usually milder compared to afibrinogenaemia, and the condition is frequently combined with a dysfibrinogenaemia that is characterised by an abnormal fibrinogen variant. Several missense mutations in the 3 fibrinogen genes have been identified as the cause of dysfibrinogenaemia and hypofibrinogenaemia that lead to abnormal gene expression resulting in the decreased fibrinogen concentration or dysfunctional fibrinogen molecules.

Therapeutic substitution with human fibrinogen concentrate can correct the haemostatic defect and arrest bleeding in patients with these fibrinogen deficiencies [5, 7, 9, 10, 11].

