3.2 Study Endpoints

3.2.1 Primary Endpoint

The primary endpoint is:

- The primary endpoint is the overall clinical assessment of haemostatic efficacy of Octafibrin in treating the first documented bleeding episode of each patient. The first bleeding episode covers the time period from the first Octafibrin infusion until 24 hours (i.e., 1 day) after the last infusion or the end of the treatment observation period, whichever comes last.

The investigator's overall clinical assessment of haemostatic efficacy for bleeding will be based on a 4-point haemostatic efficacy scale (see table below). The final efficacy assessment of each patient will be adjudicated by the Independent Data Monitoring & Endpoint Adjudication Committee (IDMEAC). The number of subjects per outcome category will be assessed in the final analysis.

Category	Definition
Excellent	Immediate and complete cessation of bleeding in the absence of other haemostatic intervention as clinically assessed by the treating physician; and/or <10% drop in haemoglobin compared to pre-infusion.
Good	Eventual complete cessation of bleeding in the absence of other haemostatic intervention as clinically assessed by the treating physician; and/or <20% drop in haemoglobin compared to pre-infusion.
Moderate	Incomplete cessation of bleeding and additional haemostatic intervention required, as clinically assessed by the treating physician; and/or between 20 and 25% drop in haemoglobin compared to pre- infusion.
None	No cessation of bleeding and alternative haemostatic intervention required, as clinically assessed by the treating physician; and/or >25% drop in haemoglobin compared to pre-infusion.

FORMA-02	JSS Medical Research - Data Management		
Statistical Analysis Plan			
Form Number: MNI-DM-BIS-01 v 6.0-T1	Current Version Number: 2.0	Previous Version Number: 1.1 9-April-2015	Date:11-July-2016

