Excellent	No post-operative bleeding or oozing that was not due to complications of surgery. All post-operative bleeding (due to complications of surgery) was controlled with Octafibrin as anticipated for the type of procedure.
Good	No post-operative bleeding or oozing that was not due to complications of surgery. Control of post-operative bleeding due to complications of surgery required increased dosing with Octafibrin or additional infusions, not originally anticipated for the type of procedure.
Moderate	Some post-operative bleeding and oozing that was not due to complications of surgery; control of post-operative bleeding required increased dosing with Octafibrin or additional infusions, not originally anticipated for the type of procedure.
None	Extensive uncontrolled post-operative bleeding and oozing. Control of post-operative bleeding required use of an alternate fibrinogen concentrate.

An overall efficacy assessment taking both the intra- and post-operative assessment into account will be adjudicated by the IDMEAC. In the event that any intra- or post-operative endpoint data differ between the investigator's assessment and the adjudicated assessment by the IDMEAC, the endpoint will be that based on the adjudicated assessments based on an agreed algorithm as indicated in the IDMEAC charter.

The surgical observation period starts with the first dose of Octafibrin administered prior to elective surgery (Day 1) and, depending on the severity of the event, will last at least 3 post-operative days for minor and 7 post-operative days for major surgeries or until the day of the last post-operative infusion, whichever comes last.

In addition, the location, severity and type of surgery will be documented. Expected and actual duration of surgical procedure and details of administered dose(s) of Octafibrin (pre-, intra- and/or post-operatively) will be recorded. Fibrinogen plasma levels (pre-, intra-, and post-operatively) will be measured. Details of concomitantly administered products (except standard anaesthesia) along with a brief narrative describing the outcome of the intervention will be recorded.

The safety endpoints are:

- Vital signs.
- Physical examination.
- Check of Wells criteria for deep venous thrombosis (DVT) and PE (pulmonary embolism).
- Routine clinical laboratory assessment, including coagulation parameters.
- Adverse events (AEs), including thromboembolic complications and early signs of allergic or hypersensitivity reactions.

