4.3 Study Duration

4.3.1 Planned Duration for an Individual Subject

For subjects receiving on-demand treatment.

- the individual **subject observation and follow-up period** for each documented episode starts with the first dose of Octafibrin administered for on-demand treatment of an acute bleeding episode (Day 1) and will be followed for up to Day 30.
- Each subject's **treatment observation period** is defined according to the severity of the event and will last at least 3 days for minor and 7 days for major bleeding episodes.

For subjects undergoing surgical prophylaxis.

- the **surgical observation period** starts with the first dose of Octafibrin administered prior to elective surgery (Day 1) and, depending on the severity of the event, will last at least 3 post-operative days for minor and 7 post-operative days for major surgeries or until the day of the last post-operative infusion, whichever comes last.

During the study observation period, enrolled patients will be treated for any bleeding episodes or planned surgeries that can be managed under the protocol. Patients may remain in the study until the 24th patient has at least one documented bleeding episode.

As many bleeding episodes or surgeries as possible occurring throughout the study observation period will be documented. Only the first bleeding episodes will be used for the analysis of the primary endpoint (see Section 3.2.1). All bleeding episodes documented in the study will be assessed as a secondary endpoint (see Section 3.2.2).

Patients who were screened for the study but do not present with a bleeding episode or planned surgery during the study observation period will be considered 'no treatment' patients.

The individual observation period by subject starts with the first dose of Octafibrin administered for on-demand treatment of an acute bleeding episode or prior to elective surgery (Day 1). Subjects enrolled will be treated for any bleeding episodes or planned surgeries during the study observation period. They may remain in the study until the 24th subject has at least one documented bleeding episode.

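### When the last post-operative infusion falls on or after post-operative day 3 (minor) or 7 (major), efficacy is rated that same day without the 24-hour follow-up given to bleeds, so a later switch to another concentrate can be missed

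*Protocol*

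**What the plan says.** **Surgery.** The post-operative rating is due on the Last Post-Operative Day. Protocol 6.1.3.3 sets this as post-operative day 3 for minor surgery and day 7 for "major surgery or the day of the last post-operative infusion, whichever comes last". SAP 4.3.1, repeated in SAP 3.2.2, gives the observation period the same end: a minimum of 3 or 7 post-operative days, "or until the day of the last post-operative infusion, whichever comes last". Protocol 6.1.3.3 adds: "The assessments performed on the Last Post-Operative Day conclude the surgical observation period". After that, only safety concerns prompt further assessment.

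**Hour of the rating.** Protocol 6.1.3.3 names the day and no hour. In the protocol's surgical flow chart, the haematologist's mark stands in the 1-hour post-infusion column of the Last Post-Operative Day.

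**Bleeds.** The rated episode runs "until 24 hours (i.e., 1 day) after the last infusion or the end of the treatment observation period, whichever comes last" (SAP 3.2.1; likewise Protocol 3.1.1 and 7.2.1).

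**Worst post-operative category.** The definition of *None* closes with: "Control of post-operative bleeding required use of an alternate fibrinogen concentrate" (SAP 3.2.2; also Protocol 7.2.2.3, Table 3).

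**What is recorded.** For surgery, Protocol 4.4.1 confines concomitant-medication recording to the surgical observation period, apart from medication used to treat a serious adverse event. Protocol 7.4.1.2 confines non-serious adverse events to the same period.

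**The concern.** The two efficacy ratings are treated differently, and neither document says why. A bleed always has a day of observation behind its final infusion. A surgical case has none if the last infusion falls on or after the day 3/7 minimum.

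In that situation the rating is closed before anyone can see whether the final infusion held. If bleeding then recurs and is treated with another fibrinogen concentrate, which Protocol 3.2 and 4.8 allow when Octafibrin has not been adequate, the event meets the definition of *None* but comes after the rating. Omitting such events can only raise the apparent surgical success rate. Efficacy in surgery is a stated secondary objective (Protocol 2.2) and may rest on as few as 4 procedures (Protocol 4.1), so a single omission would be visible in the result.

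**Working it through.** The plan gives no figure on this point to reproduce. The check compares the two timing rules, follows a late switch through the recording rules, and then asks what can be said about frequency and size.

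**1. Interval between last infusion and rating**

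| Last infusion | Surgical rating | Minimum interval required | Bleed rule |
|---|---|---|---|
| Pre-operative loading infusion only | Post-operative day 3 or 7 | About 3 or 7 days | At least 24 h |
| After surgery, before day 3/7 | Post-operative day 3 or 7 | Next calendar day or later | At least 24 h |
| On or after day 3/7 | Same day | None in the text; about 1 h by the flow chart | At least 24 h |

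Only the third row lacks follow-up.

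**2. A switch to another concentrate after the rating, in the third row**

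- *Does it move the rating day?* No. Only a further study infusion redefines the Last Post-Operative Day.
- *Is it within the post-operative period?* No. Protocol 6.1.3 ends that period on the Last Post-Operative Day.
- *Is the product recorded?* Only if it treats a serious adverse event (Protocol 4.4.1).
- *Is the bleed recorded?* Only if it is serious (Protocol 7.4.1.2 and 7.5).
- *Would adjudication see it?* The committee reviews the surgical case (Protocol 7.2.2.3), but it cannot rely on data that were not collected.

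**3. When an infusion falls due on the last scheduled day**

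Inputs: targets of 150 and 100 mg/dL and lower limits of 130 and 80 mg/dL for major and minor surgery, checked daily (Protocol 5.4.3 and 6.1.3.2); and a plasma half-life that, "under normal physiological conditions, has been estimated to be 3–5 days" (Protocol 1.1). Assumptions: every infusion reaches target exactly, there is no endogenous fibrinogen and no surgical loss, and decay is mono-exponential.

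Time from target to limit is t = T½ × log2(target/limit).

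- Major: log2(150/130) = 0.206, so t = 0.62 days at T½ = 3 and 1.03 days at T½ = 5.
- Minor: log2(100/80) = 0.322, so t = 0.97 days at T½ = 3 and 1.61 days at T½ = 5.

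The level is below the limit at every daily check if t < 1 day, that is, if T½ < ln 2 / ln(target/limit):

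- Major: ln 2 / ln(150/130) = 4.84 days.
- Minor: ln 2 / ln(100/80) = 3.11 days.

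Post-operative days on which an infusion falls due:

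| T½ (days) | Minor (to day 3) | Major (to day 7) |
|---|---|---|
| 3 | 1, 2, 3 | 1 to 7 |
| 4 | 2 | 1 to 7 |
| 5 | 2 | 2, 4, 6 |

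Sensitivity of the major-surgery result:

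- *Overshoot.* The next-day trigger disappears if the post-infusion level is at least 130 × 2^(1/T½). At T½ = 4 that is 154.6 mg/dL, 3% above target. At T½ = 3 it is 163.8 mg/dL, 9% above.
- *Endogenous fibrinogen.* Eligibility allows activity up to 50 mg/dL (Protocol 4.2). With an assumed stable baseline of 40 mg/dL, the cut-off becomes ln 2 / ln(110/90) = 3.45 days instead of 4.84.
- *Surgical consumption* acts the other way and would bring infusions forward.

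**4. Effect on the success rate**

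With 4 surgeries, one success turned to failure moves 4/4 (100%) to 3/4 (75%), a change of 25 points. The exact 95% intervals are 0.398 to 1 and 0.194 to 0.994. Under Table 6 (Protocol 9.4.2.4), a post-operative *None* is a failure when the intra-operative rating is *Good*, *Moderate* or *None*. With intra-operative *Excellent* it goes to primary adjudication.

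**5. A related inconsistency**

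The note in Protocol 6.1.3.1 for a subject needing only the first infusion says that the Last Post-Operative Day post-infusion assessments are done instead. It does not say that the subject must first reach day 3 or 7. The matching note for bleeds, in Protocol 6.1.2.1, does require the end of the observation period. Protocol 6.1.3.1 and 6.1.3.3 need to be reconciled.

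**The case against.** The strongest reply is that the day 3/7 minimum does most of the work. A reader might infer that surgery is always rated on the day of the last infusion. It is not: the rule takes the later of two dates, and an earlier last infusion is followed by a rating on a later day. This stands, and it confines the point to one case.

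A reader might also infer a rating fixed at 1 hour, taken at peak fibrinogen and so flattering the product. The documents do not support that. The hour rests on one flow-chart column, read from a text copy in which cells may have shifted; that chart also puts the hospitalisation and follow-up narrative at the end of surgery, whereas Protocol 6.1.3.3 puts it on the last day. The scale grades bleeding, oozing and dosing over the whole post-operative period, and wound haematomas and oozing are documented daily (Protocol 6.1.3.2). The rating is therefore not a reading of one moment.

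There are real safeguards. Study product is to be used whenever possible, and a further infusion of it moves the rating day. Serious events and their treatment are reported throughout participation. The adjudication committee reviews each surgical case. The flow chart also carries its adverse-event and medication arrows through to the Study Completion Visit, although Protocol 4.4.1 and 7.4.1.2 limit recording in plain terms and Protocol 6.1.4 lists neither item for that visit. Late failures therefore *can* be missed; it does not follow that they *are* missed. A non-serious switch to another product still has no assured route into the rating.

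Finally, bleeds and surgeries differ in scale, rater and success rule, and no planned analysis compares them. The timing difference is not what makes their rates non-comparable, and a 24-hour extension would not make them comparable.

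**Conclusion.** The point holds in conditional form. If the last post-operative infusion is on or after day 3 (minor) or day 7 (major), the surgical rating has no required follow-up, and a later non-serious failure treated with another concentrate can go uncounted. Any resulting bias runs in one direction, towards success.

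Frequency cannot be stated from the documents. The 4.84-day and 3.11-day cut-offs are arithmetically right under the idealised assumptions, but small departures move them. A reader might infer that this is the usual case after major surgery, because most of the 3–5 day range lies below 4.84 days. That would treat a physiological range as a uniform distribution of patients, which nothing supports. The documents also give no probability of a late switch.

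The 25-point change is what one altered result would do at the minimum of 4 surgeries, and it is subject to the adjudication cell in Table 6. It is not an expected bias. Surgical efficacy is secondary and descriptive (Protocol 9.4.2.4, SAP 8.3.5), so the primary hypothesis test is untouched. This is a worthwhile, inexpensive improvement.

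**What to change.** - In Protocol 6.1.3.3 and SAP 3.2.2 and 4.3.1, end the surgical rating window at the later of post-operative day 3/7 and 24 hours after the last post-operative infusion, which is the trial's own rule for bleeds.
- Extend the recording of other haemostatic products to the same point.
- Place the haematologist's rating there, and align the surgical flow charts in both documents.
- Reconcile the single-infusion note in Protocol 6.1.3.1 with Protocol 6.1.3.3.

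No treatment rule changes. The cost is wording in the two documents and one further contact, about a day later, for subjects infused on the last post-operative day.
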